9.7.1.6.2 SECONDARY EFFICACY ANALYSES

The MCI/Prodromal Cohort

An MMRM will be used to analyze the following secondary endpoints:

- Change from baseline in total hippocampal atrophy at 12 and 18 months of treatment in MCI/Prodromal subjects as measured by vMRI
- Change from baseline in CSF A β (1-x) after 4 weeks and 18 months of treatment in MCI/Prodromal subjects. Data from early discontinuations will also be included.

Comparisons between each treatment group and placebo will be performed.

The Mild AD Cohort

The MMRM will be used to analyze the change from baseline of derived ADCOMS at 18 months in mild AD. If there is no treatment group-by-population interaction in the overall study, the MMRM analysis will include all subjects (MCI/Prodromal or mild AD) in the overall study. Otherwise, the MMRM analysis will only include subjects in the mild AD cohort. The comparison between placebo and active doses will be performed within mild AD subjects regardless of subjects included in the MMRM analysis. Dunnett's method will be used to control for multiplicity due to multiple comparisons.

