9.7.2 Determination of Sample Size

9.7.2.1 Sample Size Rationale in the MCI/Prodromal Cohort

Primary endpoint – derived ADCOMS

The sample size and design characteristics to test the hypothesis for the primary objective based on the primary endpoint, change from baseline of the derived ADCOMS at 18 months, were determined by means of simulations. Extensive study simulations have shown that a total of 500 subjects will be sufficient to demonstrate that the most likely ED₉₀ dose achieves a 25% improvement over placebo with a probability of at least 80% in the interim and final analyses. There is at least a 90% probability of study success for the dose response scenarios

where treatment was considered to have a clinically meaningful treatment effect. Simulations have also shown that if there is no obvious dose effect, the probability of falsely claiming superiority to placebo is at most 5%.

For each of the 4 treatment groups (3 active doses and placebo) the final number of subjects per group will differ depending on the observed interim treatment responses. The simulation plan will be an appendix to the statistical analysis plan and will present further details.

vMRI

The null hypothesis is that there is no difference between active dose and placebo. There are 3 null hypotheses corresponding to 3 active doses. The alternative hypothesis is that at least 1 null hypothesis is false (1-sided). The null hypotheses will be tested using Dunnett's method with 1-sided alpha of 0.05. The statistical power was estimated through simulation for a moderate dose-response assumption that the percent reduction in change from baseline of total hippocampal volume compared with placebo would be 15%, 20%, and 25% corresponding to the 3 doses, respectively. The estimated power for the actual planned study sample size is 78% at 18 months assuming an attrition rate of 20% at 18 months. Under a stronger dose-response assumption (ie, the percent reduction in change from baseline of total hippocampal volume compared with placebo is twice as much as that in the moderate dose-response assumption), the estimated power is at least 99% at 18 months.

Amyloid PET

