9.7.2.2 Sample Size Rationale for the Mild AD Cohort

ADCOMS at Month 18

The null hypothesis is that there is no difference between active dose and placebo. There are 2 null hypotheses corresponding to 2 active doses. The alternative hypothesis is that at least 1 null hypothesis is false. The null hypotheses will be tested using Dunnett's test with 2-sided alpha of 0.05 as described for the mild AD cohort in [Section 9.7.1.6.2](#). The statistical power was estimated through simulation for the dose-response assumption that the percent reduction in change from baseline of ADCOMS at 18 months compared with placebo would be 33% and 50% corresponding to the 2 doses, respectively. The estimated power for the actual planned 200 mild AD subjects is at least 80% assuming a 2-sided alpha of 0.05.

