E2609 is a novel, small-molecule BACE1 inhibitor. Preclinical studies have shown that after oral dosing, E2609 inhibits the production of $A\beta$ 40 and $A\beta$ 42 in brain (rat and guinea pig) and in cerebrospinal fluid (CSF) and plasma (rat, guinea pig, and monkey). In humans, E2609 has been shown to inhibit BACE1 enzyme activity in CSF and lower the levels of $A\beta$, including amyloid beta monomer from amino acid 1 to x ($A\beta$ [1-x]), $A\beta$ (1-40) and $A\beta$ (1-42), in CSF both in vitro and in vivo. See the Investigator's Brochure for additional information. The target indication for E2609 is therefore treatment and disease modification of AD.

The present clinical study represents the sole Phase 2 study for the E2609 program, and is designed to establish Proof of Concept in subjects with Mild Cognitive Impairment due to Alzheimer's Disease/Prodromal Alzheimer's Disease (referred to as MCI/Prodromal throughout the protocol). The study also allows investigation of efficacy in subjects with mild dementia due to Alzheimer's Disease (referred to as mild AD throughout the protocol) to determine whether the effects of E2609 in this later stage population are comparable with those established in the MCI/Prodromal population within this same study. In the MCI/Prodromal population, Bayesian response adaptive randomization design is used with

frequent interim analyses to continually update randomization allocation based on emerging clinical endpoint data. This approach allows for ongoing assessment of drug futility or evidence of early success and can mitigate the risks associated with larger and longer studies required to demonstrate clinical efficacy by leading to more efficient study termination or early advancement to a Phase 3 program. Results from this study will guide both the decision to move into Phase 3 development and the selection of the dose strengths to be taken into Phase 3. Moreover, this study is intended to be supportive for registration in the MCI/Prodromal population.

In the MCI/Prodromal population, this study will compare placebo and 3 oral doses of E2609 (5 mg, 15 mg and 50 mg) administered once daily (QD) for 18 months. In the mild AD population, this study will compare placebo and 2 oral doses of E2609 (15 mg and 50 mg) administered QD for 18 months. To date, the longest duration of dosing with E2609 is 14 days (multiple ascending dose [MAD] Study E2609-A001-002 [Study 002]).

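### Specifying step-down Dunnett for the dose-versus-placebo tests would raise the chance of declaring the lower dose effective by about 8 points in mild AD, at the same family-wise error

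*Protocol*

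**What the plan says.** Section 9.7.1.6.2 (mild AD cohort) compares each active dose with placebo on ADCOMS at 18 months and says that Dunnett's method "will be used to control for multiplicity due to multiple comparisons". Section 9.7.2.2 repeats the choice as Dunnett's test "with 2-sided alpha of 0.05 as described for the mild AD cohort". It adds "There are 2 null hypotheses corresponding to 2 active doses" (15 mg and 50 mg) and "The alternative hypothesis is that at least 1 null hypothesis is false". The planning effects, as percent reductions in the placebo change, "would be 33% and 50% corresponding to the 2 doses, respectively". On power it states "The estimated power for the actual planned 200 mild AD subjects is at least 80" percent.

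Section 9.7.2.1 names Dunnett's method at 1-sided 0.05 for hippocampal vMRI ("There are 3 null hypotheses corresponding to 3 active doses") and says amyloid PET uses the same test. The analysis sections for those two endpoints do not mention Dunnett.

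No section says whether the single-step or the step-down version is meant. Sections 9.7.1.6 and 9.7.3 give the mild AD cohort up to two interim looks, at 60% and 80% information, with a printed first-look boundary of 0.076.

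**The concern.** An analyst following the unqualified name would ordinarily program the single-step test. That test holds every dose to the critical value for the whole family, even after the best dose has been declared positive. Step-down Dunnett is the closed-testing version. The largest statistic faces the same critical value, and the next faces a smaller one only if the first was rejected. Every single-step rejection is kept, and some are added.

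The stated powers are all for rejecting at least one null hypothesis, so they cannot show how weak the design is for the lower dose. The Introduction says the results will guide "the selection of the dose strengths to be taken into Phase 3". Whether 15 mg works as well as 50 mg bears on that, and this is where the single-step test gives up power.

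**Working it through.** **Method.** With equal arms of n, T_i = (mean difference)/(s√(2/n)). The statistics share the placebo arm (correlation 0.5), and the noncentrality is d_i√(n/2), where d_i is the difference divided by the SD. Critical values and powers were simulated, with 1,000,000 trials per scenario.

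**1. Reproduce a stated figure.** Amyloid PET is the only Dunnett calculation with all inputs printed (Section 9.7.2.1): SD 0.33, differences 0.15, 0.20 and 0.25, 100 subjects in 4 arms (25 each), 1-sided 0.05.
- d = 0.15/0.33, 0.20/0.33, 0.25/0.33 = 0.455, 0.606, 0.758
- √(25/2) = 3.536, so the noncentralities are 1.61, 2.14 and 2.68
- df = 100 − 4 = 96; critical values for 3, 2 and 1 remaining doses are 2.088, 1.938 and 1.661
- At least one rejection: 81.1%, against the stated 80%

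**2. PET, single-step against step-down.**

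| | Single-step | Step-down |
|---|---|---|
| At least one | 81.1% | 81.1% |
| Low dose | 31.8% | 42.7% |
| Middle dose | 52.3% | 59.3% |
| High dose | 72.2% | 75.1% |
| All three | 22.5% | 37.0% |

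**3. Mild AD, one analysis.** 200/3 gives about 66 per arm; df = 3×66 − 3 = 195; the 2-sided 0.05 critical values are 2.227 (two doses) and 1.972 (one dose). The placebo change and SD are not stated. A ratio of 1.03 gives the stated 80%, with d = 0.33×1.03 and 0.50×1.03, about 0.34 and 0.51.

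| | Single-step | Step-down |
|---|---|---|
| At least one | 79.9% | 79.9% |
| 15 mg | 39.2% | 47.4% |
| 50 mg | 76.5% | 77.9% |
| Both | 35.7% | 45.3% |

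Power for 15 mg over a range of ratios:
- 1.0: 37.2% to 45.1%
- 1.2: 51.9% to 60.9%
- 1.5: 73.0% to 80.5%

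With 53 evaluable per arm, back-solved again to 80%, the gain is the same.

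**4. Family-wise error, one analysis.** Under the global null it is identical for the two versions: 4.97% (two doses) and 4.96% (three). With one mild AD dose strongly effective and the other null, the error on the null dose is 4.98% for step-down and 2.69% for single-step. In no simulated trial did step-down reject fewer doses.

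**5. Mild AD with three looks (60%, 80%, 100%).** At nominal levels 0.0076, 0.0221 and 0.0423:
- global-null error is about 5.1% for both versions
- with one dose effective, the error on the null dose is 4.2% to 5.0% for step-down and 2.7% for single-step
- power for 15 mg goes from 39.2% to 47.2%, and for both doses from 35.7% to 45.2%

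The value 0.0076 is an assumption. With the printed 0.076 at the first look, the global-null error is about 9.8% under either version.

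**6. vMRI.** 500×0.8/4 = 100 evaluable per arm, if arms are equal. A ratio of 1.43, back-solved to the stated 78%, also gives over 99% when the effects are doubled, as Section 9.7.2.1 states. The low dose goes from 29.2% to 39.3%, the middle dose from 48.4% to 55.1% and the high dose from 68.0% to 71.0%.

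**The case against.** The strongest reply is that nothing here is wrong. Dunnett's method controls the error, no stated power or sample size changes, and the protocol leaves further analytical detail to the SAP, which could specify step-down without contradiction. That stands, and it is why this is an improvement and not an error. It does not remove the point, because the procedure is named in the protocol and its ordinary reading is the less powerful version.

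A reader might infer that power is lost for nothing. The documents do not support that. Single-step gives simultaneous intervals for every dose that agree with the tests, which is a legitimate reason to keep it in a dose-finding study.

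A reader might also infer that the Phase 3 dose choice hangs on these tests. It does not. The primary objective uses a Bayesian model in the MCI/Prodromal cohort that reports, for each dose, its probability of being the ED90 and of a 25% improvement. Mild AD ADCOMS is a secondary endpoint and amyloid PET an exploratory one.

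Most of the magnitudes are also conditional. The mild AD ratio is back-solved from a lower bound on power, and mild AD dropout is not stated. The vMRI figures assume equal arms, although allocation is response-adaptive and the protocol expects group sizes to differ. Only the PET figures rest entirely on printed inputs.

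**Conclusion.** The point holds as a cheap improvement. Step-down Dunnett keeps the same family-wise error level, never rejects fewer doses, and adds about 8 points to the chance of declaring 15 mg effective in mild AD (about 39% to 47%). That assumes a placebo change/SD ratio near 1.03; over ratios of 1.0 to 1.5 the gain is about 7.5 to 9 points. For PET the low-dose gain is about 11 points (32% to 43%) on printed inputs. For vMRI it is about 10 points, only under assumed equal arms.

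That the plan means single-step is the conventional reading, not a printed statement. The section on mild AD has one lower dose, so nothing follows there about several lower doses. Nor is the cohort shown to be underpowered: the powers for at least one dose are the same under both versions, and the Bayesian primary analysis is untouched. The three-look error results hold for a first boundary of 0.0076, not for the 0.076 printed.

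**What to change.** In Sections 9.7.1.6.2 and 9.7.2.2 (and the matching synopsis text), specify step-down Dunnett. For mild AD, at each look, compare the Dunnett-adjusted P value of the larger statistic with that look's boundary. Once it is crossed, compare the other dose's unadjusted P value with the same boundary.

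Before that, correct the first-look boundary of 0.076 in Sections 9.7.1.6 and 9.7.3. It exceeds the overall 0.05, and neither version controls the error with it. Recompute the boundary from the stated spending function and confirm that it is 0.0076.

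Use the same step-down wording where Section 9.7.2.1 names Dunnett for vMRI and PET. Leave the stated powers as they are.

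The cost is a wording change in the protocol and SAP and a standard programming option, with no added subjects. Single-step simultaneous confidence intervals will no longer match the rejections one to one and should be labelled descriptive. If the sponsor prefers matching intervals, it should say that single-step is kept for that reason.

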9.7.1.6.3 EXPLORATORY EFFICACY ANALYSES

An MMRM will be used to analyze the following exploratory endpoints:

- Change from baseline in the derived ADCOMS at 12 months in MCI/Prodromal and mild AD subjects
- Change from baseline in total hippocampal atrophy at 12 and 18 months in mild AD subjects as measured by vMRI
- Change from baseline in CSF A β (1-42) after 4 weeks and 18 months in MCI/Prodromal subjects. Data from early discontinuations will also be included.
- Change from baseline in CSF A β (1-x) and CSF A β (1-42) after 4 weeks and 18 months in mild AD subjects. Data from early discontinuations will also be included.

- Change from baseline in the clinical assessments: ADAS-cog, CDR, MMSE, ISLT, CBB, and FAQ at 12 weeks and at 6, 9, 12, 15, 18, 19, and 21 months in MCI/Prodromal and mild AD subjects
- Change from baseline in plasma and CSF amyloid and CSF BACE1 measurements after 4 weeks and 18 months of treatment, and during posttreatment follow-up in MCI/Prodromal and mild AD subjects
- Change from baseline in left and right hippocampal, whole brain, and total ventricular volume at 6, 12 and 18 months as measured by vMRI in MCI/Prodromal and mild AD subjects

A linear mixed-model will be used to analyze the following exploratory endpoints:

- Change from baseline in brain amyloid levels as measured by amyloid PET at 18 months in MCI/Prodromal and mild AD subjects
- Change from baseline in CSF biomarkers of neurodegeneration (eg, tau, p-tau) at 18 months of treatment in MCI/Prodromal and mild AD subjects

Data from early discontinuations will also be used as appropriate. Comparisons between each treatment group and placebo will be performed.

A linear mixed-model with repeated measures will be used to determine the relationship between the following endpoints:

- Change from baseline in the derived ADCOMS score and the change from baseline in biomarkers in CSF at 18 months in MCI/Prodromal and mild AD subjects
- Change from baseline in the derived ADCOMS score and change from baseline in imaging biomarkers (hippocampal, whole brain, and total ventricular volumes) at 12 and 18 months in MCI/Prodromal and mild AD subjects

ApoE status for heterozygous and homozygous E4 carriers will be included in the model to assess the effect of *ApoE* status in this relationship.

9.7.1.7 Pharmacokinetic, Pharmacodynamic, Pharmacogenomic, and Other Biomarker Analyses

9.7.1.7.1 PHARMACOKINETIC ANALYSES

The Safety Analysis Set will be used for individual E2609 concentration listings. The PK Analysis Set will be used for summaries of E2609 concentrations.

9.7.1.7.2 PHARMACODYNAMIC, PHARMACOGENOMIC, AND OTHER BIOMARKER ANALYSES

Pharmacodynamic, PGx, and other biomarker analyses may be performed and reported separately. Details of these analyses may be described in a separate statistical analysis plan. Please also refer to [Appendix 3](#).

Pharmacodynamic Analyses

The PD Analysis Set will be used for the summaries and analyses of PD biomarkers (CSF and plasma biomarkers, MRI endpoints). CSF A β (1-x), A β (1-42), t-tau, p-tau, and BACE1 will be assessed and data will be presented graphically. Baseline levels and changes in t-tau and p-tau will be correlated with changes in CSF A β (1-42), imaging markers, and *ApoE4* status.

Summary statistics for CSF biomarkers will be assessed for evidence of a dose relationship.

Pharmacokinetic and Pharmacodynamic Analyses

The PK/PD relationship between CSF biomarker levels and exposure to E2609 in CSF will be explored graphically and any emergent relationship will be explored through population PK/PD modeling. The PK/PD relationship between plasma PK parameters with other biomarkers may also be explored using similar methods.

Additionally, the relationship between plasma and CSF exposure to E2609 and the derived ADCOMS at 18 months, and the relationship between plasma and CSF exposure to E2609 and the change from baseline for 18 months in the ADAS-cog, the CDR, and the MMSE, will be explored graphically. Any emergent relationship will be explored through population PK/PD modeling.

Exposure-safety analyses may also be conducted.

Pharmacogenomic Analyses

Blood samples will be used to determine the *ApoE* genotype and the *NAT2* phenotype of subjects enrolled in this study. The genomic DNA samples may also be stored and used as described in [Section 9.7.1.7.2](#). Details of PGx testing may be provided and reported separately.

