9.7.1.1.1 PRIMARY ENDPOINT

- Change from baseline in the derived ADCOMS at 18 months of treatment in MCI/Prodromal subjects

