- Change from baseline in the derived ADCOMS score and the change from baseline in biomarkers in CSF at 18 months in MCI/Prodromal and mild AD subjects
- Change from baseline in the derived ADCOMS score and change from baseline in imaging biomarkers (hippocampal, whole brain, and total ventricular volumes) at 12 and 18 months in MCI/Prodromal and mild AD subjects

ApoE status for heterozygous and homozygous E4 carriers will be included in the model to assess the effect of *ApoE* status in this relationship.

Pharmacodynamic Analyses

The PD Analysis Set will be used for the summaries and analyses of PD biomarkers (CSF and plasma biomarkers, MRI endpoints). CSF A β (1-x), A β (1-42), t-tau, p-tau, and BACE1 will be assessed and data will be presented graphically. Baseline levels and changes in t-tau and p-tau will be correlated with changes in CSF A β (1-42), imaging markers, and *ApoE4* status. Summary statistics for CSF biomarkers will be assessed for evidence of a dose relationship.

Pharmacokinetic and Pharmacodynamic Analyses

The PK/PD relationship between CSF biomarker levels and exposure to E2609 in plasma and CSF will be explored graphically and any emergent relationship will be explored through population PK/PD modeling. Additionally, the relationship between CSF exposure to E2609 and the derived ADCOMS at 18 months, and the relationship between CSF exposure to E2609 and the change from baseline for 18 months in the ADAS-cog, the CDR, and the MMSE will be explored graphically. Any emergent relationship will be explored through population PK/PD modeling.

Pharmacogenomic Analyses

Blood samples will be used to determine the *ApoE* genotype and the *NAT 2* phenotype of subjects enrolled in this study. Further information is in the “Pharmacodynamic, Pharmacogenomic, and Other Biomarker Assessments” section. Details of pharmacogenomic testing may be provided and reported separately.

Safety Analyses

Evaluations of safety will be performed on the Safety Analysis Set. The incidence of AEs (including changes from baseline in physical and neurological examinations, and dermatological assessments), out-of-normal-range laboratory safety test variables, abnormal ECG findings, out-of-range vital signs, suicidality (C-SSRS), and results of the sleep questionnaire, along with the change from baseline in laboratory safety test variables, ECGs, safety MRI, and vital sign measurements will be summarized by treatment group using descriptive statistics.

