8.2 Secondary Objectives

The secondary objectives are:

1. To evaluate the effect of E2609 compared with placebo on total hippocampal atrophy at 12 and 18 months of treatment in MCI/Prodromal subjects, as measured by volumetric magnetic resonance imaging (vMRI)
2. To evaluate the effect of E2609 compared with placebo on A β (1-x) in CSF after 4 weeks and 18 months of treatment in MCI/Prodromal subjects
3. To evaluate the efficacy of E2609 compared with placebo on the derived ADCOMS at 18 months in mild AD subjects

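### The exploratory exposure-response analysis names the 18-month ADCOMS score as its outcome, while the ADCOMS endpoints and the other scales in the same passage are changes from baseline

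*Protocol*

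**What the plan says.** Under the pharmacokinetic and pharmacodynamic analyses of protocol section 9.7.1.7.2, two sets of relations are to be examined graphically, with population PK/PD modeling of whatever emerges. One is the relation between "plasma and CSF exposure to E2609 and the derived ADCOMS at 18 months". The other relates the same exposures to "the change from baseline for 18 months in the ADAS-cog, the CDR, and the MMSE". The section appears twice in the file with the same ADCOMS wording. The synopsis follows the pattern with CSF exposure only: "the relationship between CSF exposure to E2609 and the derived ADCOMS at 18 months".

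Elsewhere ADCOMS is handled as a change. The primary endpoint in section 9.7.1.1.1 is "Change from baseline in the derived ADCOMS at 18 months of treatment in MCI/Prodromal subjects". The secondary endpoint in mild AD (9.7.1.1.2) and the 12-month exploratory endpoint (9.7.1.1.3) are also changes. The closest sister analysis, which relates ADCOMS to CSF biomarkers in section 9.7.1.6.3, uses "Change from baseline in the derived ADCOMS score and the change from baseline in biomarkers in CSF at 18 months".

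**The concern.** ADCOMS is assembled from items of the ADAS-cog, the MMSE and the CDR (section 9.5.1.3.1). A single passage therefore specifies the composite as a level and its source scales as changes. An analyst following the text would plot the 18-month score itself.

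That score includes each subject's severity at entry. Entry allows an MMSE of 20 or above and an FAQ up to 20 (section 9.3.1), so entry severity can vary widely, and exposure during treatment cannot alter it. The plot would carry avoidable scatter, would not line up with the panels for the ADAS-cog, CDR and MMSE, and would not describe the quantity that the trial tests as its primary endpoint. At stake is the clarity of the exploratory exposure-response picture on the primary scale, and of any model built from it.

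**Working it through.** **1. The text.** No sample size, power or alpha is attached to this analysis, so the protocol has no figure to reproduce. The check starts from the wording.

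| Place | ADCOMS outcome |
|---|---|
| 9.7.1.1.1, primary endpoint | change from baseline |
| 9.7.1.1.2, mild AD secondary endpoint | change from baseline |
| 9.7.1.1.3, 12-month exploratory endpoint | change from baseline |
| 9.7.1.6.3, ADCOMS against biomarkers | change from baseline |
| 9.7.1.7.2 and synopsis, ADCOMS against exposure | score at 18 months, no mention of change |
| 9.7.1.7.2 and synopsis, ADAS-cog, CDR, MMSE against exposure | change from baseline |

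The ADCOMS exposure analysis stands alone.

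**2. Precision against a baseline-adjusted change.** Let ρ be the correlation between baseline and 18-month ADCOMS at a given exposure. The protocol gives no ADCOMS SD or correlation, so ρ is assumed and a range is shown. Adjusting the change for baseline leaves the same residual as adjusting the 18-month score for baseline, namely a fraction 1−ρ² of the raw variance. Hence

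Var(raw) / Var(baseline-adjusted change) = 1/(1−ρ²), whatever the ratio of the two SDs.

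- ρ = 0.4: 1/(1−0.16) = 1.19
- ρ = 0.6: 1/(1−0.36) = 1.56
- ρ = 0.8: 1/(1−0.64) = 2.78

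The ratio is never below 1.

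**3. Precision against a simple, unadjusted change.** With k = SD at 18 months / SD at baseline,

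Var(raw) / Var(change) = k²/(1 + k² − 2ρk).

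- k = 1, ρ = 0.4: 1/(2 − 0.8) = 0.83
- k = 1, ρ = 0.5: 1/(2 − 1.0) = 1.00
- k = 1, ρ = 0.8: 1/(2 − 1.6) = 2.50

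The two are equal when ρ = 1/(2k), that is at 0.5 for k = 1 and at 0.4 for k = 1.25. Below that correlation a simple change is noisier than the raw score. The precision argument therefore holds in general only for the baseline-adjusted change.

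**4. Cohort mix, if the cohorts were pooled.** The protocol does not say that they are. The MCI/Prodromal cohort has four arms and up to 500 subjects; the mild AD cohort has three arms, none at 5 mg, and about 200 subjects (sections 9.3 and 9.4.1). Equal allocation at full enrollment is assumed, although MCI/Prodromal allocation becomes response-adaptive after the first 100 subjects.

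- Per arm: 500/4 = 125 MCI/Prodromal and 200/3 = 66.7 mild AD
- Mild AD share of placebo, 15 mg and 50 mg: 66.7/(66.7 + 125) = 35%
- Mild AD share of 5 mg: 0%

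Pooling without adjustment would make the 5-mg group differ from the others in cohort alone.

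**The case against.** The strongest reply is that the phrase is shorthand. A secondary objective in section 8.2 reads "To evaluate the efficacy of E2609 compared with placebo on the derived ADCOMS at 18 months in mild AD subjects", and the matching endpoint is a change from baseline. The primary objective in section 8.1 is worded in a similar way. This stands as far as it goes: the protocol does not prove that a raw score will be analyzed. But the objectives are followed by endpoint definitions that settle their meaning. Section 9.7.1.7.2 has no such definition, and it spells out change for the other three scales, so the literal reading is at least open.

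A second reply is that the section allows details to go into a separate analysis plan, and that a population model can carry baseline and cohort as covariates. That is fair for the adjustment and for cohort handling, and their absence here is no fault. It does not cover an outcome that the protocol names itself and that differs from its own endpoint.

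Three stronger readings might be inferred, and the documents support none of them.

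- **That the analysis is the basis for choosing a dose.** The ED90 comes from the Bayesian primary analysis of the change in ADCOMS (sections 9.7.1.6 and 9.7.1.6.1). The introduction assigns Phase 3 dose selection to the study's results in general. This analysis is graphical first, with no decision rule.
- **That cohort differences will distort the relation.** That requires unadjusted pooling, which is nowhere stated. Section 9.2.3 says that the cohorts are analyzed separately for decisions.
- **That a raw score is always less precise than a change.** Against a simple change with equal SDs, this fails when the correlation is below 0.5.

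**Conclusion.** The point holds as a wording mismatch in an exploratory analysis. The outcome named for ADCOMS differs from the primary endpoint, from the other scales beside it and from the sister biomarker analysis. If the text is followed literally, the residual variance is 1.19 to 2.78 times that of a baseline-adjusted change for correlations of 0.4 to 0.8. Those correlations are assumed; the direction is not, because the ratio cannot fall below 1. Confounding through the missing 5-mg arm in mild AD would be added only under unadjusted pooling. The primary analysis and the ED90 determination are unaffected. This is a worthwhile improvement of low weight.

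**What to change.** In section 9.7.1.7.2 and in the corresponding synopsis paragraph, name the outcome as the change from baseline in the derived ADCOMS at 18 months. Add that any modeling adjusts for baseline ADCOMS and that the relation is shown by cohort; these two details could equally sit in the analysis plan. Baseline ADCOMS can be derived from scales already administered at the Baseline Visit, so no new data, visits or subjects are needed. The cost is one phrase in each place.
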